to infant cues during bottle-feeding. Indeed, in an NIH-funded, laboratory-based trial (R03-HD080730), we illustrated mothers show significantly greater responsiveness and feed their infants 26% less when using opaque, weighted bottles compared to conventional, clear bottles. While initially conceived as a promising adjunct to a larger obesity prevention approach, our laboratory findings suggest that opaque bottles may be a simple, yet potent, stand-alone tool for improving mothers' abilities to feed responsively and reducing infants' risk for overfeeding and rapid weight gain. In the proposed study, we aim to test this approach outside of the laboratory and enroll 100 new, formula-feeding mothers and infants (< 2 weeks old) into a randomized trial to examine the 12-week effects of using opaque, weighted bottles versus clear bottles for improving bottle-feeding interactions and reducing child obesity risk. We will use preestablished and state-of-the-art procedures to objectively measure infants' intake and mothers' responsiveness to infant cues (i.e., objective assessment of feeding patterns, coding of mother-infant bottle-feeding interactions) within their homes at the beginning and end of the 12-week study period. Intervention feasibility, fidelity, acceptability, and safety will be evaluated. Specific aims of the proposed research are:

AIM 1: To test the hypothesis that mothers who use opaque, weighted bottles for a 12-week intervention period will feed their infants less and be more responsive to their infants' cues compared to mothers who use clear bottles. Intake will be objectively assessed via change in bottle weight before and after feeding observations. Responsiveness to infant cues will be coded from video-records of feeding observations using the Nursing Child Assessment Parent-Child Interaction Feeding Scale.

AIM 2: To test the hypothesis that infants who are fed from opaque, weighted bottles will exhibit slower 12-week weight gain trajectories compared to infants who are fed from clear bottles. Infants' weight, length, skinfolds, and waist circumference will be measured at the beginning and end of the study; weight-forlength z-scores (WLZ) will be calculated using the WHO Growth Standards.

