#### **Statistical Considerations**

Data Analysis. All quantitative analyses will be conducted using SAS v.9.4 (SAS Institute Inc., North Carolina, USA). Oualitative interview data will be transcribed and sorted into thematic categories using constant comparison within the framework of grounded theory. We will use linear regression to model the change in infant intake and maternal responsiveness (Aim 1) and change in WLZ, skinfolds, waist circumference (Aim 2) by the primary study variable of *clear* versus *opaque* group. For Aim 3, we will examine the feasibility, fidelity, adherence, acceptability, and safety of the intervention by summarizing quantitative and qualitative data related to recruitment and retention, mothers' use of their assigned bottles, perceptions of and barriers to using the bottles, and any issues related to infant inadequate weight gain or weight loss. We will then explore whether variations in intervention feasibility, fidelity, adherence, acceptability or safety are correlated with baseline characteristics of mothers (e.g., weight status, race/ethnicity, socioeconomic status, parity, feeding practices and styles, non-maternal caregiver involvement in feeding) and infants (e.g., sex, birth weight, weight status, temperament). Finally, we will assess whether the effects of the intervention on infant intake, maternal responsiveness, and infant WLZ change are moderated by the following factors: nipple type; mothers' adherence to the intervention, race/ethnicity, parity, or feeding practices and styles; infants' sex, temperament, and timing of solid food introduction; and the extent to which non-maternal caregivers are feeding the infant. Moderation will be explored by including a group by moderator interaction term in the linear regression models used to explore Aims 1 and 2. All inferential analyses will be preceded by appropriate descriptive statistics and graphs to determine that assumptions for linear regression are satisfied.

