#### Potential Risks and Plan for Data Safety and Monitoring

**Potential Risks.** The risk involved in this study is considered minimal. Some infants or mothers may dislike using the bottles we offer during the infant-feeding study, thus may perceive the experience of using these bottles as unpleasant. It is also possible that an unintended consequence of the opaque bottles will be that mothers and caregivers underfeed their infants, resulting in inadequate growth for their infants. Some mothers may feel uncomfortable answering questions about their attitudes about and concern for their infants' feeding and weight gain patterns. Additionally, some dyads may experience discomfort related to having their feedings video-recorded or having our research staff present in their homes. There is also risk of breach of confidentiality given that video records are being collected.

**Plan for Data Safety and Monitoring.** We have developed effective procedures for protecting participants' safety and confidentiality. All participants will be assured that they have the right to opt out of any part of the study with which they feel uncomfortable. Additionally, we will check-in with mothers and infants frequently to monitor infants for insufficient growth (<20-30g/day) or weight loss. The research assistants will monitor the participants for adverse events, including inadequate infant growth.

The PI will hold primary responsibility for ensuring that the proposed trial is conducted according to protocol and carrying out the above data safety and monitoring plan. However, the PI will also identify a local pediatrician to serve as the Data and Safety Monitor (DSM) for the proposed study. Given that feeding interactions and infant growth are of primary interest, we will identify a local pediatrician with particular expertise in this area and have several pediatricians affiliated with our research center who have this expertise. Once appointed, the DSM will help ensure that our protocol and intervention and assessment of adverse events are in line with local pediatric providers' usual care plans. The DSM will meet with the PI and Co-I's quarterly to review and evaluate the accumulated study data for participant safety, study conduct and progress, and alignment with pediatric providers' usual care plans. The DSM will also ensure that all enrolled families have a pediatrician with whom they regularly consult to add an additional layer of monitoring and protection.

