Infants who exhibit slower than expected growth will be referred to their pediatrician or emergency services for further consultation and will be removed from the study if the PI and/or DSM deem study participation harmful to the infant or family.

We will also employ strategies we have used in previous studies to minimize discomfort, including having familiar research staff present in the homes during assessments, and moving to another room or outside the home (if another room is not available) during video-recorded feeding interactions. The PI has significant expertise in coding video-recorded feeding interactions and ensuring mother and infant comfort and confidentiality during this process. Furthermore, all research assistants will be trained to ensure that assessments are conducted in a professional and nonjudgmental manner.

Adverse events determined by the PI to be unanticipated problems involving risks to subjects or to others will be reported by the PI to the IRB within 10 days. Adverse events that are reviewed by the PI and not determined to be unanticipated problems involving

risks to subjects or to others will be reported per IRB policy at the time of continuing review.

All study personnel will be informed by the PI about any unanticipated problems involving risks to subjects or to others. If any protocol changes are needed, the PI will submit a modification request to the IRB. Protocol changes will not be implemented prior to the IRB approval unless necessary to eliminate apparent immediate hazards to the research participants. In such a case, the IRB will be promptly notified of the change following implementation (within 10 working days). Protocol adherence will be monitored by the PI during bi-monthly meetings with the research assistants. If the PI is made aware of an unanticipated protocol deviation, the PI will report this deviation to the IRB within 10 days.

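### Infants removed for harmful slow growth leave the study with no further growth measurement planned, so the week-12 growth comparison loses outcomes for a reason tied to the outcome itself

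*Combined protocol and SAP*

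**What the plan says.** The safety section (Potential Risks and Plan for Data Safety and Monitoring) recognises as a possible harm that "an unintended consequence of the opaque bottles will be that mothers and caregivers underfeed their infants, resulting in inadequate growth for their infants". Staff are to "monitor infants for insufficient growth (<20-30g/day) or weight loss". Infants growing more slowly than expected are referred to their pediatrician or emergency services, and they "will be removed from the study if the PI and/or DSM deem study participation harmful to the infant or family". No separate step covers stopping the bottles while staying in follow-up, and no measurement after removal is described.

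Aim 2 predicts that "infants who are fed from opaque, weighted bottles will exhibit slower 12-week weight gain trajectories". The Data Analysis paragraph of Statistical Considerations fits a linear regression of "change in WLZ, skinfolds, waist circumference (Aim 2) by the primary study variable" of clear versus opaque group. It gives no analysis population and no method for missing outcomes. Growth is also checked at brief visits in weeks 2 and 6 (Assessments and Measures). Drop-outs and their reasons are tracked, and Aim 3 summarises problems of inadequate gain or weight loss.

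**The concern.** Removal is triggered by growth, and growth is the Aim 2 outcome. An infant who leaves before week 12 has no change score, so a regression on the available changes drops that infant. The loss therefore depends on the outcome. Because the plan predicts slower gain under the opaque bottle and names underfeeding as a risk of that bottle, removals are expected more often in the opaque arm. Trimming the slow tail more heavily in that arm pulls its mean up and shrinks the estimated difference.

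The 20% attrition allowance under Power calculations replaces numbers but does not correct a loss of this kind. The trial would also not learn whether a removed infant's growth recovered after the bottles were stopped, which matters for judging whether the harm is reversible.

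**Working it through.** **Inputs from Power calculations.** SD of WLZ 1.0; correlation between baseline and week 12 0.45; n = 100; difference 0.59; 80% power; alpha .05. Assumed here: 1:1 allocation (50 per arm) and a two-sided test, because neither is stated.

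**Reproducing the plan's figure.** SD of change = 1.0 × sqrt(2 × (1 − 0.45)) = 1.049. Detectable difference = (1.960 + 0.842) × 1.049 × sqrt(2/50) = 0.588, which agrees with 0.59. Power at 0.59 is 80.3%.

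**Assumptions about removal.** The documents give no removal rate. The monitoring figure is in g/day and is itself a range, so WLZ change is only a proxy for the trigger. Take changes as normal with SD 1.049, mean 0 in the clear arm and −0.59 in the opaque arm, and remove infants below a common cut-off c = −0.59 + 1.049 × z(f), where f is the fraction of opaque infants removed. For an arm with mean m, let a = (c − m)/1.049 and λ = φ(a)/(1 − Φ(a)). The retained mean is m + 1.049 × λ and the retained SD is 1.049 × sqrt(1 − λ(λ − a)).

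**Case A: removal tracks the final change exactly.**

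| | f = 5% | f = 10% |
|---|---|---|
| Cut-off c | −2.315 | −1.934 |
| Clear infants removed | 1.4% | 3.3% |
| Retained mean, opaque / clear | −0.476 / 0.037 | −0.385 / 0.079 |
| Observed difference | −0.513 | −0.464 |
| Retained SD, opaque / clear | 0.944 / 1.006 | 0.885 / 0.970 |
| Retained n, opaque / clear | 47.5 / 49.3 | 45.0 / 48.4 |
| SE of difference | 0.198 | 0.192 |
| Power | about 73% | about 65–67% |

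The SE is sqrt(0.944²/47.5 + 1.006²/49.3) = 0.198, and likewise for the second column. The normal approximation Φ(|difference|/SE − 1.96) gives 73.5% and 67.7%. Simulated t-tests come out slightly lower, hence the rounded values. Keeping the SD at 1.049 after the tail has been cut off would give 66% and 56%, which overstates the loss.

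**Case B: removal follows interim growth correlated 0.5 with the final change.** The shift in each retained mean is halved:
- f = 5%: opaque −0.533, clear 0.019, difference −0.552, power about 74%.
- f = 10%: opaque −0.488, clear 0.039, difference −0.527, power about 70%.

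**Discretionary removal.** If only half of the infants with WLZ change below −2.5, −2.0 or −1.5 are removed, the difference has size 0.56, 0.54 or 0.51, with power 78%, 76% or 72%. The corresponding opaque-arm removal rates are 1.7%, 4.5% and 9.6%, against 0.4%, 1.4% and 3.8% in the clear arm.

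**The case against.** The strongest reply is that removal will probably be rare. Slow growth alone leads to referral. Removal needs a judgement by the PI and/or DSM that participation is harmful, and the eligibility criteria already exclude preterm, low-birth-weight and slow-growing infants. Removal must also come before week 12 and cannot follow the final value exactly, so Case B is nearer to practice than Case A. Its bias is 0.04 to 0.06 WLZ. All of this stands, and it limits the size of the problem.

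Four stronger readings are tempting, and the documents do not support them:
- A reader might infer that every slow grower is removed. The text makes removal conditional.
- A reader might infer that the safety signal is lost. The triggering event has already been observed by then. It is covered by adverse-event monitoring, quarterly DSM review, the week 2 and 6 growth checks, the tracking of drop-out reasons and the Aim 3 summary. What is missing is the later course and the week-12 value.
- A reader might infer that these infants carry the Aim 2 effect. That effect is a mean shift across the arm. Even in the 10% scenario of Case A, 0.464/0.59 = 79% of it remains.
- A reader might take the excess of removals in the opaque arm as documented. It is an inference from the hypothesis and the stated risk.

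Nor does the bias favour the intervention on every count. A difference pulled toward zero works against the investigators' own Aim 2 hypothesis, while it makes average growth under the opaque bottle look less slow than it is.

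The rule also concerns harm from participation to infant or family, so for some families the home visits may be part of what has to stop. The fix must allow for that.

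**Conclusion.** The point holds as a gap in follow-up and analysis that should be closed. Followed as written, the plan loses the week-12 outcome for a reason tied to that outcome, probably unevenly between arms, and nothing in the analysis section addresses it. The likely direction is toward no difference.

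On the assumed removal of 5% or 10% of opaque infants, −0.59 shrinks to between −0.55 and −0.46 across Cases A and B, and power falls from 80% to between about 74% and 65%. The smaller loss is the more plausible, and with very few removals the effect would be slight. These figures rest on assumed removal rates, a common cut-off, normal changes, 50 infants per arm and WLZ change as a stand-in for a g/day trigger. The direction depends on removals being more frequent in the opaque arm.

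**What to change.** Leave the clinical removal decision unchanged with the PI and DSM, and change only data collection and analysis:
- State that stopping the study bottles does not by itself end growth follow-up. Where the mother agrees, and the PI and DSM do not consider the visits themselves harmful, keep the remaining scheduled growth measurements, with week-12 weight and length as the minimum.
- Analyse these infants in the arm to which they were randomised.
- Report growth-related removals by arm under Aim 3. Counts and reasons are already to be collected, so the split by arm is the addition.
- For a removed infant with no week-12 value, add a sensitivity analysis that uses the available week 2 and week 6 growth and applies a range of pessimistic shifts. Assigning the lowest change seen in the arm would be arbitrary and would ignore those earlier measurements.

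The cost is a few sentences in the protocol and consent form plus one sensitivity analysis, and the visits are already scheduled and budgeted. One limit should be stated: infants followed after stopping the bottles may drift toward clear-arm growth. The result is then an as-randomised estimate, and it need not restore −0.59.
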